In all three arms, the three-day diet intervention will be preceded and followed by three days of self-conducted elimination diet. The pre-intervention diet will encourage participants to eat a healthy, light diet for three days (basic instructions: eat only fresh raw or cooked fruits and vegetables (preferably organic), whole grains and eggs; drink 8 glasses of water a day; avoid or eliminate alcohol, caffeine, sugar, processed foods, dairy, red meat, and gluten). The post-intervention diet will instruct participants to gradually return to eating solid foods, and limit strenuous exercise (basic instructions: follow a diet similar to the pre-intervention elimination diet; day 1 after the intervention: eat fruits & green vegetables, and drink 8 glasses of water; day 2 add in: nuts, gluten-free grains like whole oats, quinoa, or brown rice; day 3 add in: organic meats, fish, & gluten-containing grains).

Biological samples and self-reported outcomes will be collected at four time points: baseline (prior to the first elimination diet period), pre-intervention (after the elimination diet and before the three-day intervention), post-intervention (after the intervention), and 14-day post-intervention. At each time point, participants will complete questionnaire on quality of life (PROMIS - Global Health Scale, which is an NIH measure on an individual's' overall physical and psychological well-being; see appendix) and collect their own saliva and stool samples. Participants will be given self-administered toolkits and be taught how to collect the samples at their first lab visit. At each of the four time points, the research assistant will coordinate the collection of cheek swabs and bloodspot samples. Stool samples will be collected using a premoistened wipe, with written instructions provided to participants, and both stool and saliva samples will be collected by the participant at home, then provided to the research assistant at their next visit.

Over the course of the study, participants will be instructed to keep a diet diary days one through nine to record their dietary intake of each day (diet diary forms with instructions attached), as well as fill out a modified version of the PROMIS Global Health Scale. During the intervention period, the research team will also contact the participants to check in with them. Participants will not need to record diet data for the fourteen day post intervention period.

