At the conclusion of the study, participants will bring back the final biological samples (stool wipe and saliva), provide the fourth bloodspot sample, and be debriefed about the purposes of the study.

The biological samples collected will then be processed and assayed for microbiome, methylation, inflammatory markers, and glycemic markers.

All questionnaire data will be stored in a REDCap database, separate from screening surveys, which are not to be used as study data. REDCap is a secure, web-based application designed to support data collection and management activities for research studies, and these databases will be hosted by the Feinberg School of Medicine.

DATA AND SPECIMEN BANKING:

If fewer participants drop out than anticipated, any excess blood/stool/saliva samples will be banked for later assay. All such specimens will be stored at the Center for Population Epigenetics.

Consent forms and demographic information will be added to Study Tracker, per FSM participant tracking policy.

The specimens will be stored in a -80C freezer at the Center for Population Epigenetics, Northwestern University, located at [name]. The specimen can be accessed through the principal investigators and lab manager.

The procedure to release specimen and data:

- 1. Requester submits application to principal investigators with specific aims and specimen number and list;
- 2. The principal investigators review and approve the request of specimen and related data;
- 3. The request is forwarded to lab manager, who will conduct the sample recording and retrieval from the freezer.
- 4. The data associated with specimens related to the study including patient ID, date of collection, time of collection, and time point, will also be released.

SHARING OF RESULTS WITH PARTICIPANTS:

We have no plans to share individual participants' results. Aggregate data will be available to participants upon request.

STUDY TIMELINES:

Recruitment and data collection will last for three months. Each participant will stay in the study for 21 days (if they choose to complete the study). Primary analyses are expected to be

INCLUSION AND EXCLUSION CRITERIA:

Participants have to meet the all of the following criteria to participate in the study:

- 1. Subjects considered as healthy by the investigator based on medical history and completion of the screening questionnaire.

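### The handover rule for home-collected stool and saliva makes holding time before the freezer differ by time point, so within-arm before-after microbiome statements are not protected

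*Protocol*

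**What the plan says.** All of the collection rules are in the protocol section Procedures Involved.

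- **Kits:** "Participants will be given self-administered toolkits and be taught how to collect the samples at their first lab visit".
- **Home collection and handover:** "both stool and saliva samples will be collected by the participant at home, then provided to the research assistant at their next visit".
- **First two time points:** "baseline (prior to the first elimination diet period), pre-intervention (after the elimination diet and before the three-day intervention". The other two are after the intervention and 14 days after it.
- **Diet periods:** "the three-day diet intervention will be preceded and followed by three days of self-conducted elimination diet".
- **Staff contact:** "At each of the four time points, the research assistant will coordinate the collection of cheek swabs and bloodspot samples".
- **Closing visit:** "At the conclusion of the study, participants will bring back the final biological samples (stool wipe and saliva), provide the fourth bloodspot sample".

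Three other sections bear on the point. Study Endpoints names change in gut microbiota among the primary endpoints. Study Timelines gives each participant 21 days in the study. Data and Specimen Management and Confidentiality puts samples in a -80C freezer once they reach the laboratory. It lists the label items as participant ID, collection date, collection time and time point. Receipt and freezing times are not among them. The protocol states neither a home storage condition nor a maximum holding time for these samples.

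**The concern.** A microbiome change within an arm is a difference between samples taken at two time points. If the two samples waited for different lengths of time before freezing, any alteration during the wait is added to that difference and cannot be told apart from the effect of the diet. Here the wait is set by a stated rule tied to the visit schedule, so it varies with time point by design and not by chance.

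The endpoint is worded as changes that may occur after juice fasting, which invites a before-after reading in the fasting arm. About six completers per arm are expected (three men and three women, 18 in all), so descriptive within-arm statements are likely. No later analysis can equalise the holds, and the listed label items would not even show how long each sample waited.

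**Working it through.** The protocol prints no holding time, so there is no figure to reproduce. The schedule can be rebuilt from its parts.

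**Inputs**
- Pre-intervention elimination diet: 3 days.
- Intervention: 3 days.
- Last time point: 14 days after the intervention.
- First possible home collection: after the initial visit, because kits and training are given there.

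**Day numbers, with baseline as day 0**
- Pre-intervention: 0 + 3 = day 3.
- Post-intervention: 3 + 3 = day 6.
- Closing visit: 6 + 14 = day 20.

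Day 0 to day 20 is 21 calendar days, which matches the stated stay. The diet diary for days one to nine also fits (3 + 3 + 3 = 9). The stay leaves at most about one day for a separate baseline handover, and none is described.

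**Formula:** holding time = day of handover minus day of collection. A sample taken shortly before the visit at which it is handed over counts as 0-1 day.

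| Sample | Natural reading: later samples handed over at their own visit | Literal reading: each sample kept to the following visit |
|---|---|---|
| Baseline | 3 - 0 = about 3 days | 3 - 0 = about 3 days |
| Pre-intervention | 0-1 day | 6 - 3 = about 3 days |
| Post-intervention | 0-1 day | 20 - 6 = about 14 days |
| Final | 0-1 day | 0-1 day (brought to the closing visit) |

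**Differences in hold between time points**
- Baseline against final: about 2 to 3 days longer for baseline on both readings.
- Baseline against post-intervention: about 2 to 3 days longer for baseline on the natural reading; 14 - 3 = 11 days longer for post-intervention on the literal one.
- Pre- against post-intervention: comparable, within about a day, on the natural reading; 11 days apart on the literal one.

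**What this does to the estimates.** Let h(t) be the average alteration after t days of holding. The observed within-arm change from time point 1 to time point 2 is then the true change plus h(hold 2) - h(hold 1). The second part is zero only if the holds are equal or holding has no effect. In a difference between arms the same second part appears in both arms and is subtracted out. The cancellation is exact only if holding acts alike on samples from each arm and participants in each arm keep to the same timing, so between-arm comparisons are largely, not perfectly, protected.

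The form and size of h are not in the protocol, so no numerical bias can be given.

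**The case against.** The strongest objection is that the timeline is inferred. The protocol does not say that the visit after kit hand-out is the pre-intervention visit. Height is taken at the initial intake and weight and waist at every time point, which would fit an intake separate from baseline. If baseline bloodspots were taken at a short second contact, the home samples could be handed over there and the 3-day hold would disappear. This stands as a limit: the 3 days follow from the visits described and would fail if there were an undescribed visit or pick-up.

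A reader might also infer that baseline is always the longest-held sample, by at least three days. The protocol does not support that. Direct handover is explicit only for the final sample, and on the literal reading post-intervention is held longest. It would likewise be tempting to treat the pre- to post-intervention pair as a safe fallback, but on that reading its two holds differ by about 11 days.

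Harm is also not demonstrated. The kit, the premoistened wipe and the written instructions are not available to this review. They could provide for a preservative, home freezing or the timing of collection, and so reduce the alteration or the gap. That is right as to size. It does not remove the stated handover rule, which yields unequal holds on either reading.

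Finally, the stated objective is a comparison of three arms, and a baseline-to-post change already includes the elimination diet, so pre-intervention is the more natural reference. Both points limit the consequence. Neither protects a before-after statement within an arm.

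**Conclusion.** The point holds as a minor but real design weakness. The handover rule, read with the kit hand-out at the first visit and the closing-visit handover, makes holding time depend on time point: about 3 days against 0-1 day for baseline and final on the most natural reading, and about 3, 3, 14 and 0-1 days if applied literally throughout.

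This rests on three assumptions: no undescribed baseline handover, baseline collection close to the start of the elimination diet, and a last time point 14 days after the intervention. The label list in the specimen section calls the fourth time point 3 days post. On that basis the literal post-intervention hold would be about 3 days instead of 14, but the 21-day stay fits 14.

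The conclusion is confined to within-arm change. The documents do not show that the microbiome results are biased, in which direction, or by how much, and the randomised between-arm comparison of change is largely unaffected.

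**What to change.** - Replace the next-visit rule with one maximum interval from collection to handover and one home storage condition, the same at all four time points. Later samples would be collected shortly before their own visit, and the baseline sample dropped off or picked up within the same interval.
- Add date and time of receipt or freezing to the sample record. Collection time alone does not give the hold.
- Report holding time by time point.
- Limit within-arm microbiome statements to pairs of time points whose recorded holds are comparable, and check this for the pre- to post-intervention pair before relying on it.

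The cost is one short extra handover per participant, up to 30 in all at full enrolment, and one extra data field. The randomised comparison does not change.

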Fruits and vegetables have also been studied for their antioxidant effects due to the phenolic and prebiotic compounds inherent to the foods. The phenolic and micronutrient compounds contribute to the effectiveness of fruits and vegetables as antioxidants. A 2013 study on the effect of increasing fruit and vegetable consumption found increased levels of -tocopherol, lutein, beta carotene, beta cryptoxanthin, and ascorbic acid through diet intervention. Increasing the amount of antioxidants in the diet can combat the effects of oxidative stress which contribute to the development of chronic disease. The beneficial compounds of fruits and vegetables remain obtainable in pressed fruit/vegetable juice. A 2017 study found pure pressed fruit and vegetable juices contained the necessary polyphenols and vitamins found in whole fruits and vegetables to maintain the positive relationship between fruit/vegetable consumption and lower incidence of chronic noncommunicable disease. Similar to studies with whole fruit, participants consuming pure fruit/vegetable juices had lower levels of lipid peroxidation and higher levels of most plasma/serum antioxidant vitamins. Therefore, pressed fruit/vegetable juices are an appropriate method through which to study the effects of fruit/vegetable consumption on the development of chronic disease.

Despite the popularity of 3-day juice fast, there is little existing literature delineating the effects of the diet intervention over other fasting protocols. 3-day juice fast programs qualify as a fast under the definition of fasting due to the low caloric intake of the participant. The 3-day juice fast program we will be utilizing provides approximately 800 -900 kcal per day, 60% and 70% less than the average recommended daily intake for women and men age 19-30, respectively. The purpose of this study is to delineate the mechanism through which juice fasting interventions affect change in methylation, gut microbiome, and inflammation markers.

STUDY ENDPOINTS:

The primary endpoints of the study are changes in epigenetic markers, gut microbiota, and biomarkers of inflammation and insulin resistance that may potentially occur after juice fasting. Secondary goals of the study include providing a foundation for future studies to examine the mechanisms of the intervention and test the intervention in a larger scale.

STUDY INTERVENTIONS / INVESTIGATIONAL AGENTS:

Group 1: Juice Fasting

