- 2. Subjects who, according to the investigator, can and will comply with the requirements of the protocol and are available for all scheduled visits at the investigational site.
- 3. Healthy male or female aged between 18 and 35 (included) years
- 4. $18.5 \le BMI \le 30 \text{ kg/m}^2$
- 5. Ability to give their informed consent in writing

Individuals meeting any of the following criteria may not participate in the study:

- Documented history of previous cardiovascular disease, including CHD (angina, myocardial infarction, coronary revascularization procedures or existence of abnormal Q waves in the electrocardiogram (EKG)), stroke, syncope, and clinical peripheral artery disease with symptoms of intermittent claudication.
- 2. Severe medical condition that may impair the ability of the person to participate in a nutrition intervention study (e.g. digestive disease with fat intolerance, advanced malignancy, or major neurological, psychiatric or endocrine disease including diabetes).
- 3. Daily use of any prescription or non-prescription medication that has a high likelihood of impacting systemic inflammation (e.g. non-steroidal anti inflammatories or steroids), blood sugar control (e.g. medication for diabetes) or the human microbiome (e.g. antibiotics).
- 4. Any other medical condition thought to limit survival to less than 1 year.
- 5. Known immunodeficiency disorder
- 6. Illegal drug use or chronic alcoholism or total daily alcohol intake >80 g/d.
- 7. Difficulties or major inconvenience to change dietary habits
- 8. Impossibility to follow an elimination or juice fast diet, for religious reasons or due to the presence of disorders of chewing or swallowing (e.g., difficulties to consume nuts)
- 9. A low predicted likelihood to change dietary habits according to the Prochaska and DiClemente stages of change model (Nigg, 1999).
- 10. History of food allergy with hypersensitivity to any of the components of the juice or diet
- 11. Patients with an acute infection or inflammation (e.g., pneumonia) are allowed to participate in the study 3 months after the resolution of their condition.
- 12. Dietary restrictions due to medical (including allergies), religious, or other concerns

13. Any diagnosis of allergic rhinitis, eczema, asthma, or inflammatory bowel disease (e.g. ulcerative colitis or Crohn's) from a health professional

VULNERABLE POPULATIONS:

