Diet intervention: Fasting and juice cleanse diets over short periods are generally safe, but may cause some minor discomfort during the study period. For those on restricted intake diets, several minor adverse effects may occur and include constipation, headache, muscle cramps, diarrhea, general weakness, and rash. Most of these are short-lived, and are generally alleviated by adequate fluid intake and other minor diet modifications. The restricted diet may lead to decreases in glucose levels; this risk will be mitigated by screening participants for the exclusion criteria of diabetes, hypoglycemia, steroid-dependent diseases and use of medications that impact on blood sugar such as sulfonylureas and insulin.

Blood Spot: There is a small risk that the puncture associated with the blood spot may cause bruising or infection at the site of the needle insertion.

Weight, height and waist circumference measurements: There is no physical risk involved in measuring weight, height, and waist circumference but there is a risk of embarrassment or discomfort at being measured in one's underclothes.

Behavioral and psychological questionnaires: These carry a minimal risk for emotional discomfort and stress.

Participants will be fully informed of all of these risks during the informed consent process and be given the opportunity to withdraw from the study at any time without any further obligation. No data will be collected until informed consent has been obtained. We expect all of these risks to be temporary, and to quickly subside after the study is concluded.

Efforts to minimize risk are as follows:

Dietary intervention: Participants will be instructed to speak to the research associate or principal investigator if they experience discomfort, such as constipation, diarrhea, weakness, muscle cramps, or dizziness. There is instruction provided with the juice cleanse on how to address any potential side effects stemming from the diet. Participants will be told that their participation is voluntary and they can choose to withdraw from the study at any time without any further obligation.

Blood spot: Bloodspot collection will be done as professionally and comfortably as possible. Blood is collected for the in-person assessments in a sterile manner to reduce the threat of infection. Likewise, pressure is applied to the puncture site to prevent hemorrhage and ecchymosis.

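### Eating disorders are named in no eligibility criterion and no described screening item, so a past or normal-weight case can be randomised to 800-900 kcal/day

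*Protocol*

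**What the plan says.** Protocol, Inclusion and Exclusion Criteria:

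- Inclusion 1 admits "Subjects considered as healthy by the investigator based on medical history and completion of the screening questionnaire".
- Inclusion 3 and 4 set age 18 to 35 and BMI 18.5 to 30 kg/m².
- Exclusion 2 removes people with a "Severe medical condition that may impair the ability of the person to participate in a nutrition intervention study". Its examples include "advanced malignancy, or major neurological, psychiatric or endocrine disease including diabetes".
- Exclusion 7 removes people with "Difficulties or major inconvenience to change dietary habits", and exclusion 9 those with "A low predicted likelihood to change dietary habits according to the Prochaska and DiClemente stages of change model".
- Exclusion 12 removes people with "Dietary restrictions due to medical (including allergies), religious, or other concerns".
- Exclusion 13 bars any diagnosis of certain allergic and bowel conditions, with no severity threshold.

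Recruitment Methods describes campus flyers and an online REDCap screener that includes SF-36 general health questions and demographics.

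Procedures Involved assigns two of the three arms to 800-900 kcal/day for three days. All arms have three days of elimination diet before and after, and keep a diet diary for days one to nine. Weight and waist are measured at each time point (Physiologic Measures).

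Risks to Participants covers physical effects of the diet, bruising or infection from the finger prick, embarrassment at being measured, and questionnaires, of which it says "These carry a minimal risk for emotional discomfort and stress". The safety-monitoring section adds possible side effects that include moodiness and difficulty thinking. Neither section mentions disordered eating.

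**The concern.** The trial invites young adults, mostly students, to eliminate foods, record intake, be weighed repeatedly and, in two arms, eat very little for three days. The Background describes the juice programme's energy as "60% and 70% less than the average recommended daily intake for women and men age 19-30, respectively". A history of an eating disorder is a foreseeable reason why this could be unsafe for an individual.

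Exclusion 2 turns on severity and on impaired ability to take part. Someone with a past eating disorder, or one at normal weight, may be neither severely ill nor unable to follow a juice or low-calorie diet. What is at stake is participant safety. Eligibility belongs in the protocol, so the gap cannot be left to a later analysis document.

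**Working it through.** **Step 1. Which written criteria could reach an eating disorder?**

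| Criterion | What it can catch | What it leaves |
|---|---|---|
| Inclusion 1 (judged healthy) | A current case that appears in the medical history or is volunteered | Past illness seen as resolved; undisclosed illness |
| BMI at least 18.5 | Underweight people | Anyone at normal weight |
| Exclusion 2 | Severe or major psychiatric disease that may impair participation | Past, milder or non-impairing cases |
| Exclusion 12 | Some people already restricting their diet for other concerns | Past cases; patterns not reported as a restriction |

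Each criterion removes part of the group. None removes a past case, and none reliably removes a normal-weight one.

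**Step 2. Does the described screening supply the information?** Only SF-36 health questions and demographics are described. No item on eating behaviour or eating-disorder history is mentioned, so inclusion 1 depends on what medical history brings out.

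**Step 3. Does the Protocol use broader wording elsewhere?** Yes. Exclusion 13 bars any health-professional diagnosis of, for example, eczema, and exclusion 1 bars a documented history of cardiovascular disease. Eczema is therefore excluded by name, while past anorexia is left to a severity judgement.

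**Step 4. Energy level.** The six juices, one of each per day, give 140 + 170 + 120 + 130 + 120 + 140 = 820 kcal, which is inside the stated 800-900. The caloric-restriction menus are stated as 862 to 889 kcal/day. I take those totals as stated. The third menu's listed items add to 162 + 75 + 229 + 353 = 819 against 889 stated, which is a separate matter to reconcile.

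**Step 5. Chance of enrolling at least one affected person.** Inputs: up to 30 randomised to three arms (Procedures Involved). Equal allocation is assumed, in line with the equal expected completers per arm, so 30/3 = 10 per arm and 20 in the two restricted arms. The documents give no prevalence, so *p*, the proportion affected among those enrolled, is assumed to lie between 1% and 10%. Treating participants as independent, the chance is 1 − (1 − *p*)^*n*:

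| *p* (assumed) | *n* = 30 | *n* = 20 (two restricted arms) | *n* = 10 (juice fast) |
|---|---|---|---|
| 1% | 26% | 18% | 10% |
| 3% | 60% | 46% | 26% |
| 5% | 79% | 64% | 40% |
| 10% | 96% | 88% | 65% |

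For example, 1 − 0.97^20 = 0.456.

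**The case against.** The strongest reply is that the plan is not unguarded. The investigator must judge each person healthy, major psychiatric disease is a named example, and exclusion 12 may remove current restrictors. Participants are contacted on each intervention day, physicians can be paged, withdrawal is open at any time and the restricted diet lasts three days. The screener's described content is not stated to be exhaustive, and the instrument itself is not shown. The consent pages were removed from the copy reviewed, so nothing can be said about them. The prevalence range is assumed, one rate is used for both sexes, and having a history does not mean being harmed. All of this stands and limits the size of the point. It does not supply a criterion that reaches a past or normal-weight case.

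A reader might infer more than the text supports in four ways:

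- **That no criterion keeps such people out.** Step 1 of the working shows that four criteria may catch some of them.
- **That exclusions 7 and 9 favour people drawn to restriction.** Both are adherence filters on difficulty or unlikelihood of changing diet. Neither measures a wish to restrict, and exclusion 7 could equally remove people with rigid eating habits.
- **That both restricted arms are at about 820 kcal.** That sum belongs to the juice arm only.
- **That one case would distort the 14-day comparison.** One person is 1/6, or 17%, of a six-completer arm, but no effect size supports a claim of distortion. The primary endpoints are changes, with each participant's own baseline available, so an unusual baseline level does not by itself bias the contrast.

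**Conclusion.** The point holds as a safety gap in eligibility. Nothing in the Protocol is miscalculated or contradictory here. Its written criteria and described screening simply allow a past or normal-weight eating disorder through to an arm at 800-900 kcal/day. Under the assumed 1% to 10% prevalence among those enrolled, equal allocation and independence, the chance of at least one such participant is 26% to 96% among 30 and 18% to 88% among about 20 in the restricted arms. The lower end depends entirely on the assumed prevalence. The range describes enrolment and says nothing about the probability of harm or about bias in the results. The correction is cheap and worth making.

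**What to change.** 1. Add to the exclusion list, in the same form as exclusion 13: *any diagnosis of an eating disorder, current or past, from a health professional*.
2. Add a matching self-report item to the REDCap screener.
3. Name disordered eating as a risk in Risks to Participants.

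The cost is a short protocol amendment and one screener item. A few volunteers are lost and the sample becomes slightly narrower; the Protocol gives undergraduate enrolment as 8,353, so recruitment should bear this. Undisclosed cases will still be missed, because the screen relies on self-report.
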